2.5 Remote Unscheduled Visits

Unscheduled visits may be performed remotely anytime to assess or follow up adverse events or at the request of the subject, parent, caregiver, or investigator, or if additional study product is needed before the next scheduled remote study visit. The date and reason for the remote unscheduled visit must be recorded in the source documentation.

Noninterventional unscheduled visit procedures will be conducted as appropriate according to the protocol schedules of activities and the data recorded in the subject's source documents.

2.6 Early Discontinuation

Subjects who discontinue early from the study while restrictions are in place will have a remote early discontinuation visit approximately 14 days after their last dose of study product. Noninterventional early discontinuation procedures will be conducted according to the protocol schedule of activities and as described in [Section 2.4](#). Subjects will be

encouraged to return to the study site to complete all early discontinuation procedures when regular study site visits resume, unless consent is withdrawn.

Subjects with unresolved adverse events at early discontinuation while restrictions are in place or who had gastrointestinal (GI) adverse events of interest will have safety follow-up ([Section 2.8](#)).

The criteria for early discontinuation due to missed doses while restrictions are in place will be based on the guidance provided later in this appendix ([Figure 1](#), [Table 1](#)). Depending on the reason and number of missed doses, certain subjects who miss doses and stop study product dosing when the restrictions are in place will not be discontinued early from the study. Such subjects may reinitiate dosing after study site visits resume. When regular study site visits resume, the regular protocol criteria for early discontinuation due to missed doses will apply.

2.7 Study Exit

Subjects who complete study treatment (initial dose escalation, up-dosing, and maintenance, which may be extended when restrictions are in place) will continue blinded study treatment and have remote study visits every 4 weeks until regular study site visits resume. Study exit will not occur until regular study site visits resume. Study exit procedures will be conducted in accordance with the study protocol.

2.8 Safety Follow-Up

In the event remote procedures are implemented, safety follow-up procedures will be conducted in accordance with the study protocol, except that subjects who discontinue due to GI adverse events will have remote study visits instead of study site visits when required, and no symptom-directed physical examinations will be performed.

Subjects or parents/caregivers of subjects who had GI adverse events of interest will be asked to complete the Pediatric Eosinophilic Esophagitis Symptom Scores version 2.0 (PEESS v2.0) per protocol.

3 TREATMENT COMPLIANCE

Accountability for the study product will be performed to document compliance with the dosing regimen. During remote study visits, subjects or parents/caregivers will be asked to return the study diary, all used study product packaging, and any unused capsules/sachets to the study site. If the return of these items is not feasible until the next study site visit, subjects or parents/caregivers will be asked to send photographs of the study diary (relevant pages), used study product packaging, and unused capsules/sachets to the study site for interim reconciliation with the study diary. Physical study product accountability and reconciliation with the study diaries will be performed after the materials are received at the study site. New study diaries will be dispensed as needed following completion of a remote

study visit. Used study product packaging and unused capsules/sachets will not need to be stored at 2°C to 8°C.

Subjects or parents/caregivers will be asked to bring study diaries, used study product packaging, and unused capsules/sachets to the next study site visit if the return of these items to the study site is not feasible while restrictions are in place. Study site personnel must make reasonable efforts to obtain these items from subjects or parents/caregivers who do not return them at the next study site visit.

4 SAFETY CONSIDERATIONS

4.1 Dose Adjustment

[figure not shown]
The study product dose level may be continued or reduced, or the dose withheld per investigator judgment based on considerations including allergy symptoms, flare of atopic disease unrelated to study product, intercurrent illness, treatment period (up-dosing vs maintenance), and access to local medical services.

The decision to reduce a dose level when a study site visit is not possible requires discussion and approval from the medical monitor and should occur as soon as possible to ensure timely dispensation of the study product. The reduced dose level will continue until study site visits resume and dose re-escalation can be attempted under medical supervision at the study site.

4.2 Missed Doses

Subjects or parents/caregivers will be instructed to contact the study site by the second day of consecutive missed doses if a second consecutive missed dose is anticipated. A remote unscheduled visit will be conducted to determine the reason for the missed doses (eg, adverse events, noncompliance) and to assess the safety of resuming the next dose at home. Access to local medical services should also be considered. The decision to resume study product dosing at a lower dose level after at least 2 consecutive missed doses should be made as soon as possible following discussion and approval from the medical monitor. If the consecutive missed doses were due to allergic adverse events and the dose level is assessed as not tolerated, dosing at the same dose level should not resume until regular study site visits resume.

Procedures for missed consecutive doses of study product when study site visits cannot be conducted are described in [Figure 1](#) and [Table 1](#). Subjects who stop study product dosing and do not discontinue early from the study may reinitiate dosing under medical supervision at the study site after study site visits resume and following discussion and approval from the medical monitor as described in [Table 2](#). Until study site visits resume, unscheduled visits should be performed monthly to review adverse events and concomitant medications (at minimum).

Figure 1: Procedures for Missed Consecutive Doses of Study Product

The guidance for 1 missed dose or 2 missed consecutive doses assumes that the current dose level is assessed as tolerated if dosing is continued at the current dose level.

[1] At investigator discretion, the subject may be observed by video call during and after administration of the next dose of study product at home.

Table 1: Description of Actions for Missed Consecutive Doses of Study Product

Missed Doses	Action
1 dose for any reason [1]	Resume next dose at current dose level at home.
2 consecutive doses for any reason [1]	Complete a remote study visit by the second consecutive day a dose is anticipated to be missed. If dosing can resume the next day, resume next dose at current dose level at investigator discretion. If a third consecutive dose is likely to be missed, follow action for missing 3 consecutive doses for any reason.
3-4 consecutive doses for any reason	Complete a remote study visit by the second consecutive day a dose is anticipated to be missed. Consider resuming next dose at ≤ 50% of previous dose (rounded down to the nearest feasible whole dose) at home if considered safe and following discussion and approval from the medical monitor. At investigator discretion, the subject may be observed by video call during and after administration of the next dose of study product. If continued dosing is assessed as not safe or dosing cannot resume by the day after 4 consecutive missed doses, stop study product dosing and inform the medical monitor. Subject may remain in the study and reinstitute dosing when study site visits can resume and following discussion and approval from the medical monitor.

Missed Doses	Action
≥ 3 consecutive doses on 3 occasions due to noncompliance	Stop study product dosing and discontinue the subject early from the study.
5-7 consecutive doses due to noncompliance ≥ 5 consecutive doses due to reasons other than noncompliance (eg, adverse event, epidemic- or pandemic-related reasons)	Stop study product dosing and inform the medical monitor. Subject may remain in the study and reinitiate dosing when study site visits can resume and following discussion and approval from the medical monitor.
> 7 consecutive doses due to noncompliance	Stop study product dosing and discontinue the subject early from the study.

[1] The guidance assumes that the current dose level is assessed as tolerated if dosing is continued at the current dose level.

Table 2: Reinitiation of Study Treatment After Stopping Study Product

Number of Days Since Last Dose	Action [1]
≤ 14 days during any period	Resume dosing per protocol [2]
> 14 days during initial dose escalation	Reinitiate dosing from initial dose escalation day 1
15-30 days during up-dosing or maintenance	Reinitiate up-dosing at 1 mg
> 30 days during up-dosing or maintenance	Reinitiate dosing from initial dose escalation day 1

Resumption of dosing under medical supervision at the study site requires discussion and approval from the medical monitor.

[1] Additional procedures for subjects who stopped study product dosing for > 14 days are as follows:

- Confirm that the subject has no clinically significant change in health status (eg, severe or uncontrolled asthma, eosinophilic esophagitis or other eosinophilic gastrointestinal disease, chronic or recurrent gastrointestinal adverse events of unknown etiology) or any other health condition that would preclude participation in the study, in the opinion of the investigator.
- Obtain medical monitor approval before reinitiating dosing.
- When up-dosing is reinitiated, dose escalation may resume per protocol.

[2] Subjects who completed day 1 but not day 2 of initial dose escalation at the time remote procedures were implemented will repeat day 1 of initial dose escalation.

5 STATISTICAL METHODS

Changes to the statistical methods and data presentations for reporting the study due to any restrictions will be detailed in the statistical analysis plan.

Limits to the prespecified maximum duration of up-dosing and maintenance periods for subjects to meet the criteria of responders at the exit food challenge will continue to apply, with the exception of any duration of time affected by the restrictions as defined by the first and last consecutively affected study visits. For instances of multiple distinct durations of

restriction, the maximum duration of the up-dosing and maintenance periods will be extended by the cumulative sum of these distinct durations of affected study visits.

Subjects who discontinue early from the study for any reason before completing their scheduled exit food challenge, including due to the restrictions, will be counted as nonresponders in an intent-to-treat analysis, and may also be excluded from an alternative sensitivity analysis of the primary and prespecified secondary endpoints as appropriate.

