10 STATISTICAL METHODS

10.1 Statistical and Analytical Plans

The statistical methods and data presentations for reporting the study will be described in detail in the statistical analysis plan.

Randomization will be central and treatment allocation will be 2:1 (AR201 or placebo). Randomization will be stratified by baseline reactivity (tolerant or intolerant) to baked egg in an open baked whole egg food challenge at screening. Subjects who tolerate approximately 2000 mg cumulative baked egg protein without dose-limiting allergy symptoms will be considered baked egg tolerant. Subjects who do not complete the screening open baked whole egg food challenge for reasons other than dose-limiting symptoms and who have a clear clinical history of tolerance to baked egg may be considered baked egg tolerant after discussion with the medical monitor. All other subjects will be considered baked egg intolerant.

Data for demographic and baseline characteristics, efficacy, and safety will be summarized by treatment group (AR201 or placebo). Summary statistics will include the mean, number

of observations, standard deviation, median, minimum and maximum values for continuous variables, and frequencies and percentages for categorical variables.

Statistical significance is defined as $p < 0.05$ and tests will be 2-sided, unless otherwise specified. CIs will be calculated at the 95% level, reflecting a 2-sided type I error of 0.05.

The statistical methods and statistical analysis plan may be affected by a pandemic, epidemic, or other emergency not related to the study as described in [Appendix 3](#).

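### Read literally, Appendix 3 Section 5 puts the responder time limit out of reach for some subjects restarted during up-dosing, although Sections 2.3 and 2.4.2 of that appendix extend their treatment

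*Protocol*

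**What the plan says.** **Main text of the protocol.** Sections 3.1 and 5.2.3.2 require a subject to get to 300 mg/day no later than 40 weeks after day 1, and otherwise to discontinue. Section 5.2.3.2 gives 22 weeks as the shortest possible up-dosing period. Section 10.5.1 defines response by the exit challenge result alone, and anyone who leaves before that challenge is a nonresponder. Section 10.1 then says "The statistical methods and statistical analysis plan may be affected by a pandemic, epidemic, or other emergency not related to the study" and points to Appendix 3.

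**Appendix 3, keeping and restarting subjects.** Section 2.6 says that "certain subjects who miss doses and stop study product dosing when the restrictions are in place will not be discontinued early from the study". Table 1 in Section 4.2 adds: "Subject may remain in the study and reinitiate dosing when study site visits can resume and following discussion and approval from the medical monitor". Table 2 sets the restart level. After 15 to 30 days off product in up-dosing or maintenance it is "Reinitiate up-dosing at 1 mg"; after more than 30 days it is "Reinitiate dosing from initial dose escalation day 1". A footnote adds: "When up-dosing is reinitiated, dose escalation may resume per protocol". Sections 2.3 and 2.4.2 lengthen treatment and up-dosing for delay caused by the restrictions and give no cap.

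**Appendix 3, scoring.** Section 5 says that limits to the "maximum duration of up-dosing and maintenance periods for subjects to meet the criteria of responders at the exit food challenge will continue to apply". The exception is "any duration of time affected by the restrictions as defined by the first and last consecutively affected study visits", summed where there is more than one such period.

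**The concern.** Two parts of Appendix 3 pull against each other for the same subject. The conduct sections let a subject who stopped product come back, start again from the bottom of the dose ladder, and take the extra time needed. The scoring section gives back only the time between the first and last affected visits. The repeated up-dosing happens on site after visits have resumed, so on the plain wording it falls outside that span and is charged to the subject.

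Table 4 in the main text lists failure to reach 300 mg/day in 40 weeks under tolerability of study product. A restart under Appendix 3 Table 2 is not in itself a sign of intolerance. Without the appendix it would not arise, because main-text Table 16 discontinues subjects after 15 or more missed days. At stake is the primary endpoint: for a restarted subject, responder status could turn on how many weeks had been used before the stop and not on the exit challenge.

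**Working it through.** **Inputs**
- Dose levels (Section 5.2.3.2, Table 3): 12 levels from 1 to 300 mg, so 11 steps of 2 weeks.
- Up-dosing limit: 40 weeks (Sections 3.1 and 5.2.3.2).
- Maintenance maximum: 12 + 4 = 16 weeks (Section 3.1).
- Group sizes: 56 and 28 (Section 10.3).

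**The plan's own figure.** 11 × 2 = 22 weeks, which matches the stated minimum.

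**Current rule, literal reading.** Let t be the unaffected weeks used before the stop and R the exempt span, with the restart at the end of that span.
- Limit: week 40 + R.
- Earliest 300 mg dose: week t + R + 22.
- Slack: (40 + R) − (t + R + 22) = 18 − t.

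R cancels, so the length of the restriction does not matter. The limit is missed when t exceeds 18.

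| Position at the stop | Slack with no stop | Slack after restart |
|---|---|---|
| 240 mg, week 20 | 40 − (20 + 2) = 18 | 18 − 20 = −2 |
| 200 mg, week 30 | 40 − (30 + 4) = 6 | 18 − 30 = −12 |
| 160 mg, week 36 | 40 − (36 + 6) = −2 | 18 − 36 = −18 |

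**How firm is 18?**
- If the span ends at the last affected visit and the restart is at the next two-week visit, 2 more weeks are charged and the threshold is 16.
- Repeating initial dose escalation adds 2 days.
- Using the 3-day window on the final visit only gives 154 − 3 = 151 days, or 21.6 weeks, and a threshold of 18.4. Shortening all 11 intervals by 3 days gives 121 days, or 17.3 weeks, and a threshold of 22.7.
- Main-text Table 16 allows re-escalation by one level per week after gaps of 5 to 14 doses. If that pace applied to a subject last at 240 mg, regaining 300 mg would take 10 × 1 + 1 × 2 = 12 weeks and the threshold would be 28. Appendix 3 Table 2 covers longer gaps and speaks of reinitiating up-dosing, so the 2-week schedule is the more natural reading.

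**Maintenance restarts.** These subjects had already reached 300 mg/day in time. If the repeated 22 weeks counted, they would make 22 + 22 = 44 weeks of up-dosing against 40, or 22 weeks against the maintenance maximum of 16. Section 5 does not say whether they count.

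**Effect of one rescored subject.** 1/56 = 1.8 percentage points in the AR201 group; 1/28 = 3.6 in the placebo group.

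**The case against.** The strongest reply is that the text does not force the literal reading. Table 4 counts the 40 weeks as weeks of up-dosing, not from day 1, and Appendix 3 Table 2 speaks of reinitiating up-dosing. A fresh 40-week clock is therefore possible. Section 5 also leaves open which visits count as affected, so on-site visits that repeat earlier doses because of the restriction might be included. Both points stand. A reader might infer that such a subject can never be a responder, and the documents do not support anything so categorical. Against these readings, Section 5.2.3 fixes day 1 as the first day of randomized treatment, no reset is stated anywhere, and a span bounded by first and last affected visits does not naturally reach visits held on site after restrictions end.

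A second reply is that the detail belongs in the statistical analysis plan, to which Section 5 refers. That would hold if Section 5 stopped there, but it goes on to fix the limit and its exception itself.

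A third is that treatment continuation and responder scoring may differ by design, or that Section 5 caps the extension in Section 2.4.2. The rule does apply alike to both blinded arms. But if Section 5 is a cap, a subject past the threshold is restarted on at least 22 weeks of escalation only to be discontinued, and is still a nonresponder.

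Finally, the case is uncommon. Continued home dosing is the default during restrictions, and a restart needs a gap of more than 14 days and medical monitor approval. This stands and limits the weight of the point.

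**Conclusion.** The point holds as an inconsistency to be settled. It rests on three assumptions: 40 weeks counted from the original day 1, an exemption limited to the affected-visit span, and re-escalation on the 2-week schedule. Under these, a subject restarted during up-dosing misses the responder limit once more than about 18 unaffected weeks have been used, or about 16 with a two-week gap before the restart. That conflicts with the extension the same appendix grants for treatment.

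Two further inferences should be resisted. The documents give no count of such subjects, which is probably small, so no loss of power can be claimed. Nor do they show that subjects restarted from maintenance fail the limit; Section 5 is silent on them, and the amendment should settle it. This is a minor correction, but it bears on how the primary endpoint is scored.

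**What to change.** Add to Appendix 3 Section 5:

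> For subjects restarted under Table 2 after more than 14 days off product, the maximum up-dosing duration is further extended by (a) any time from the last affected visit to the restart and (b) the scheduled re-escalation time to the dose level held before the stop (2 weeks per dose level, plus the repeated initial dose-escalation days if applicable). Holds or reductions for intolerance during re-escalation still count toward the limit. Subjects who had reached 300 mg/day within the limit before the stop need not meet it again, and their re-escalation time does not count toward the maintenance maximum.

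Cross-refer to this from Section 10.5.1.

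For dose level number L in Table 3, item (b) adds 2 × (L − 1) weeks, so slack becomes 18 − t + 2 × (L − 1):
- 240 mg (L = 11) at week 20: 18 − 20 + 20 = 18.
- 200 mg (L = 10) at week 30: 18 − 30 + 18 = 6.
- 160 mg (L = 9) at week 36: 18 − 36 + 16 = −2.

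These equal the no-stop values, so this is not a new 40 weeks: the third subject, who was going to miss the limit anyway, still does. The match is exact when the stop falls at the start of a dose level. Otherwise up to one two-week interval already served at that level is not credited. Item (a) removes the 16-versus-18 ambiguity, and counting holds for intolerance keeps the limit's role as a tolerability criterion.

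The cost is this short text and one cross-reference, with no new procedures or data. The downside is slightly longer allowed treatment for a few responders, which Appendix 3 Section 2.3 already permits.

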Adverse event or intercurrent illness	
Subjects must discontinue early for any intolerable adverse event that may lead to undue risk if study treatment were continued, such as the following:
 
 • Life-threatening symptoms, including anaphylaxis resulting in hypotension, neurologic compromise, or mechanical ventilation related to study treatment or food challenge. • Severe dose-related symptoms that require intensive therapy (per investigator assessment, but may include interventions such as IV epinephrine, intubation, or admission to an intensive care unit) or are recurrent. 
Subjects must discontinue early for any adverse event that meets the early discontinuation criteria for study product tolerability or delays as follows:
 
 • Tolerability of study product: 
 – Dose-limiting or moderate symptoms at ≤ 1 mg or severe symptoms at any dose on initial dose-escalation day 1; dose-limiting, moderate, or severe symptoms on initial dose-escalation day 2 – Unable to reach the 300 mg/day dose within 40 weeks of up-dosing • Use of rescue medications: 
 – Treatment with epinephrine, beta-agonist, oxygen, IV fluids, > 2 doses of antihistamines, and/or glucocorticosteroids at ≤ 1 mg study product or for severe symptoms at the 2 mg dose on initial dose-escalation day 1 or 2 – Treatment with 3 or more doses of epinephrine for an event of dose-related symptoms anytime • Dose adjustment of study product: 
 – Unable to escalate the dose level after 3 consecutive failed attempts with at least 2 weeks between each escalation attempt – Unable to tolerate 3 attempts at dose reduction after mild or moderate symptoms, or unable to tolerate 1 attempt at dose reduction after severe symptoms • Missed ≥ 15 consecutive days of study product dosing due to any circumstances (eg, as part of the treatment for an intercurrent adverse event). Missed doses per dose adjustment guidelines in Section 8.7.3.2 are allowed. 
Subjects must discontinue early for any intolerable adverse event that cannot be ameliorated using adequate medical intervention or that in the opinion of the investigator or sponsor may lead to undue risk if study treatment were continued, such as the following:
 
 • Poor control or persistent activation of secondary atopic disease (eg, atopic dermatitis, asthma). • Development of biopsy-documented eosinophilic esophagitis.

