
Category Reason	Comment
Use of prohibited medication	Prohibited concomitant medications are listed in Section 7.4 .
Pregnancy	Pregnancy will be followed to delivery or until termination of the pregnancy (Section 8.7.7.2).
Death	
Investigator decision	Investigators may elect to discontinue a subject's study treatment if they decide it is in the subject's best interest. Select this category if adverse events/intercurrent illness, use of prohibited concomitant therapy, pregnancy, death, or noncompliance do not apply and the subject or parent/caregiver preferred the subject to continue treatment.
Major noncompliance with protocol	The medical monitor or investigator may request early discontinuation in the event of a major protocol deviation, lack of cooperation, or noncompliance. Noncompliance with study product is defined as missed doses for > 7 consecutive days (except for management of intercurrent illness) or missed doses for ≥ 3 consecutive days on 3 occasions, unless the dose was withheld for an adverse event or study product dispensing error (Section 8.7.5).
Dropout	
Parent/caregiver or subject decision	Active discontinuation choice by the parent/caregiver or subject. Subjects may permanently discontinue study treatment anytime for any reason. Do not select this category if any other category applies.
Sponsor-Initiated	
Sponsor discontinuation of study	The sponsor reserves the right to terminate the study anytime for any reason as described in Section 13.6 . The sponsor will end this study following completion of the study objectives, or earlier if deemed necessary.
Loss to Follow-Up	
Loss to follow-up	Cessation of subject participation without notice or action. Loss to follow-up procedures are described in Section 5.6 .

IV, intravenous.

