10.2 Analysis Populations

The intent-to-treat (ITT) population (ie, full analysis set) will be defined as all subjects who receive any part of one dose of study product. The ITT population will be used for all efficacy analyses unless otherwise specified, and analyzed according to randomized treatment. If no subjects receive the incorrect treatment, the ITT population will be the same as the safety population.

The completer population will be defined as all subjects in the ITT population who complete study treatment and have an evaluable exit DBPCFC (completion of at least the dried egg white food challenge day).

The per protocol population may be defined if it is sufficiently different from the completer population. The per protocol population will include all subjects in the completer population who have no major protocol deviations.

The safety population will be defined as all subjects who receive any randomized study treatment (ie, who receive any part of one dose of study product and complete one study visit). The safety population will be used for all safety analyses and analyzed according to treatment received.

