2 ENROLLMENT AND STUDY PROCEDURES

2.1 Recruitment, Screening, and Enrollment

The sponsor will notify study sites when recruitment, screening, and enrollment of subjects is suspended.

An exception to suspension of screening and enrollment is as follows: subjects who complete the screening open baked whole egg food challenge before remote procedures are implemented may return to the study site to complete the double-blind, placebo-controlled food challenge (DBPCFC) per protocol and enroll in the study if eligible. However, continued participation in the study will be per investigator and subject or parent/caregiver decision, based on the ability to attend study site visits and understanding the potential impact of the restrictions on study conduct.

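### Does Appendix 3 commit the trial to a sensitivity analysis that cannot show the effect of pandemic-related losses?

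*Protocol*

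**What the plan says.** Appendix 3, Section 5 opens by handing the matter on: "Changes to the statistical methods and data presentations for reporting the study due to any restrictions will be detailed in the statistical analysis plan". It then names one group, "Subjects who discontinue early from the study for any reason before completing their scheduled exit food challenge, including due to the restrictions", and attaches two consequences. These subjects are nonresponders in an ITT analysis, and they "may also be excluded from an alternative sensitivity analysis of the primary and prespecified secondary endpoints as appropriate".

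The first consequence repeats the main text. Sections 10.3 and 10.5.1 already treat early discontinuation before the exit challenge as nonresponse.

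Other places that bear on the point:

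- Section 10.2: "The completer population will be defined as all subjects in the ITT population who complete study treatment and have an evaluable exit DBPCFC". The same section makes ITT the default for efficacy, and Section 10.5 assigns no analysis to the completer population.
- Section 5.3, Table 4: "Subjects must discontinue early for any adverse event that meets the early discontinuation criteria for study product tolerability or delays as follows". The criteria that follow include poor tolerability, use of rescue medication and failed dose escalation. The dropout row reads "Active discontinuation choice by the parent/caregiver or subject". No row is specific to pandemic restrictions.
- Appendix 3, Section 2.1, on subjects caught late in screening: "continued participation in the study will be per investigator and subject or parent/caregiver decision, based on the ability to attend" study site visits.
- Appendix 3, Section 4.2: "A remote unscheduled visit will be conducted to determine the reason for the missed doses".

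**The concern.** A section about restrictions should, one would think, offer an analysis that shows what the restrictions did. Counting a subject who left because a site closed as a treatment failure dilutes the observed effect, and a reader will want to know by how much.

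The group named in Appendix 3 is wider than that. It mixes restriction losses with subjects who stopped because they could not tolerate the product or could not escalate, which are outcomes of treatment. If the whole group is removed, those left are nearly the completer population of Section 10.2. The result then differs from ITT even when nobody was lost to the restrictions, and unequal dropout between arms can move it either way. Because Table 4 has no restriction row, such a loss might also be filed under a general heading and be hard to separate later.

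At stake would be the reading of a supportive result: a change from ITT could be credited to the restrictions when it came from ordinary discontinuation.

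**Working it through.** **1. The plan's own figure.** Section 10.3 gives 56 AR201 and 28 placebo subjects, 60% versus 25%, two-sided alpha 0.05, and 89% power.

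- Pooled rate: (56 × 0.60 + 28 × 0.25)/84 = 40.6/84 = 0.483
- SE under the null: √[0.483 × 0.517 × (1/56 + 1/28)] = 0.1157
- SE under the alternative: √(0.60 × 0.40/56 + 0.25 × 0.75/28) = 0.1048
- Power: Φ[(0.35 − 1.96 × 0.1157)/0.1048] = Φ(1.18) = 88.0%

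Exact enumeration of the uncorrected chi-square test gives 88.5%. The 89% is reproduced closely enough, and the choice of a supportive analysis set does not enter it.

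**2. Inputs for an illustration.**

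- Other discontinuation in AR201 and placebo, dA and dP, is taken as already inside the 60% and 25% as nonresponse. The protocol plans no dropout rate. Section 1.1 reports withdrawals before maintenance in the largest US egg study: 5 of 40 (12.5%) on active and 2 of 15 (13.3%) on placebo. Here that would be 56 × 0.125 = 7 and 28 × 0.133 = 3.7 subjects.
- Restriction loss r is not given. It is assumed at 0 to 20%, equal by arm and unrelated to outcome.

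**3. Formulas (percentage points).**

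- ITT: 35 × (1 − r)
- Excluding restriction losses only: 35.0 for every r
- Excluding all discontinuers: 60/(1 − dA) − 25/(1 − dP). Here r cancels, because it reduces responders and remaining subjects in the same proportion.

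With 5/40 and 2/15, the last gives 60/0.875 − 25/0.867 = 68.57 − 28.85 = 39.7.

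| r | ITT | Restriction-only exclusion | Gap from ITT | All discontinuers excluded | Gap from ITT |
|---|---|---|---|---|---|
| 0% | 35.0 | 35.0 | 0 | 39.7 | 4.7 |
| 5% | 33.25 | 35.0 | 1.75 | 39.7 | 6.5 |
| 10% | 31.5 | 35.0 | 3.5 | 39.7 | 8.2 |
| 20% | 28.0 | 35.0 | 7.0 | 39.7 | 11.7 |

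So the premise is right: only the narrower exclusion isolates the restriction effect.

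**4. Does the wider exclusion mislead?** At the cited withdrawal rates the response ratio is 68.57/28.85 = 2.38, against 60/25 = 2.40. With 25% response in both arms it gives 28.57 − 28.85 = −0.3 points. That is rescaling, with no spurious benefit. Larger shifts need unequal dropout, which is assumed here:

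| dA / dP | Excluding all | Same, with 25% in both arms |
|---|---|---|
| 15% / 5% | 70.59 − 26.32 = 44.3 | 29.41 − 26.32 = +3.1 |
| 5% / 15% | 63.16 − 29.41 = 33.7 | 26.32 − 29.41 = −3.1 |
| 20% / 20% | 75.00 − 31.25 = 43.75 | 0 |
| 20% / 10% | 75.00 − 27.78 = 47.2 | 31.25 − 27.78 = +3.5 |
| 30% / 10% | 85.71 − 27.78 = 57.9 | 35.71 − 27.78 = +7.9 |

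This is the known behaviour of any completer-type analysis, and the direction depends on which arm loses more.

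**5. What the text fixes.** Set against these numbers, the wording commits the trial to very little. The exclusion is permitted, to be used where appropriate, and the section's first sentence sends restriction-related methods to the SAP. An SAP that excluded only restriction losses would comply fully. The section also states no purpose for the alternative analysis, so it does not promise to isolate restriction losses and then fail to do so.

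**6. How many subjects could be affected.** Appendix 3 works to keep restriction cases out of the group altogether:

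- Treatment is extended (Section 2.3).
- Food challenges are postponed and completed within 3 months after regular site visits resume (Section 2.4).
- Subjects who finish treatment stay on blinded product until exit is possible (Section 2.7).
- Five or more missed doses for pandemic-related reasons do not force discontinuation (Section 4.2, Table 1).
- The limits on period length are lengthened by the restricted time (Section 5).

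**The case for a change.** The best case for the concern is that the protocol does more than stay silent. It names a set, and the set is an awkward one for its section. The protocol also separates restriction causes from others elsewhere: the paragraph just before isolates restricted time, and the missed-dose table in Appendix 3 distinguishes noncompliance from pandemic-related reasons. Only the sensitivity-analysis sentence merges them. Choosing the narrower set in advance would also prevent a choice made after results are known.

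Part of this stands. Read literally, the sentence does not separate the two kinds of loss, and an SAP author would do well to separate them. But naming the widest group that may be excluded does not require excluding all of it. Removing every discontinuer is a common check beside a conservative nonresponder analysis. Its overlap with the completer population is redundancy, not error, and since Section 10.5 gives that population no analysis, this clause may be what provides for one.

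The point about recording reasons is inference. Table 4 lists primary reasons, and the case report form is not shown and may hold more detail. Sites already establish why doses were missed, although that is not the same as recording why a subject left.

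**Conclusion.** The concern does not hold. The protocol fixes the primary ITT rule, which counts every early discontinuer as a nonresponder. It leaves the make-up of one optional supportive analysis to the SAP, which is the ordinary place for it. Nothing here is stated wrongly, contradicted or fixed badly, and the preferred narrower exclusion is already allowed.

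In size, the primary test and the 89% power do not depend on this choice. If all discontinuers were excluded at the cited near-equal withdrawal rates, the supportive difference would be 39.7 points against 35.0, almost entirely rescaling. Restriction losses of 5% to 20% would dilute the ITT difference by 1.75 to 7.0 points, and would do so whichever set the sensitivity analysis used.

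These figures assume restriction losses equal by arm and unrelated to outcome, and they let withdrawals before maintenance in another study stand in for all discontinuation before the exit challenge. The larger shifts shown rest on assumed unequal dropout. The conclusion rests on the wording of the protocol and not on those rates.
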